7.3. IV opioids use endpoints

This section describes the handling of missing data for the IV opioids (IVO) use endpoints of:

- Cumulative IV opioid consumption while hospitalized;
- Cumulative IV opioid in the first 24 hours;
- Hourly IV opioid in the first 48 hours;
- Daily IV opioid use.

The study site staff will monitor and record all IV opioids used during the study, based on directions provided in the protocol. We do not expect to have an entire missing record for any administration of IVO, but scenarios below describe the derivation of the IVO use endpoints when one or more fields in an individual record are missing:

- Missing final stop date and time (start date/time present) for the final IVO administration:

If the start date with or without the corresponding start time for the final IV opioid dose is known but the corresponding stop date and/or time are missing, rules defined for handling of missing values/censoring (see Table 8) for the endpoint of time to discontinuation of IV opioids will be used to define the stop date and/or time for the final IV opioid dose.
- Missing start and/or stop time, but the start and stop date, route of administration, opioid dose amount and unit of IV opioid is recorded:

Depending on the route of administration, the start and/or stop time will be imputed. Typically bolus injections have a total maximum duration of 15 minutes. Missing stop or start time for a bolus injection will be imputed accordingly from the available start or stop time, respectively. For continuous infusions with a missing stop time, the start time for the subsequent infusion will be imputed as the stop time for the previous infusion. For continuous infusions with a missing start time, the stop time of the preceding infusion will be used. When prior or subsequent continuous infusions are not present, then 0:00 will be used as the start time and 23:59 will be used as the stop time. If both start and stop times are missing for a bolus injection, then 12:00 (24-hr clock) noon will be used as the start time and 12:15 as the stop time.
- Dosage for any IV opioid dose missing:

For any administration of IV opioid for which the opioid dose amount is missing, the primary analysis of IV opioid use endpoints (Cumulative use, daily use, and hourly use from 4-hour interval data for first 48 hours), will not use any imputation for the missing IV opioid dose amount, and the record will be excluded. Therefore the primary analysis of IV opioid used-related endpoints will be based only on the available IV opioid dosage

data with no imputation. The derivation of IV opioid use endpoints is provided in Appendix 10.1.

7.4. Time to discontinuation of IV opioids

Time to discontinuation of IV opioids is defined as the difference in hours between the time and date of completion of the last administration of IV opioid and the time and date of initiation of the first infusion (loading dose) of study drug. A bolus injection of an IV opioid and a continuous infusion of IV opioid can occur simultaneously. Therefore, care needs to be taken when identifying the date and time of completion of the last administration of IV opioid.

Table 8. Handling of Missing Data and Censoring Rules for Time to Discontinuation of IV opioids

Scenarios	Censored? (Yes/No)	Computation of Time to Discontinuation of IV opioid (in hours)
(i) Death	Yes	
Time to discontinuation of IV opioids
 
= STOP – START; where
 
STOP = Date and time of subject's death
 
START = Date and time of start of the first infusion (loading dose) of study drug

(ii) Latest IV opioid start date and time are recorded. Stop date is recorded but stop time is missing	No	
Time to discontinuation of IV opioids
 
= STOP – START; where
 
STOP = 23:59 on the recorded date of the last IV opioid if the latest IV opioid is a continuous infusion OR STOP = 15 minutes after the start time if the latest IV opioid is a bolus injection.
 
START (for treated subjects) = Date and time of the start of the first infusion (loading dose) of study drug.
 
START (for randomized but not treated subjects) = 12:00 (24 hr. clock) on the date of randomization.

(iii) Latest IV opioid has start date and time recorded but stop date and time are missing (subject did not discontinue from study)	Yes	
Time to discontinuation of IV opioids
 
=STOP – START; where
 
STOP = Start date and time of latest IV opioid.
 
START (for treated subjects) = start date and time of the first infusion (loading dose) of study drug.
 
START (for randomized but not treated subjects) =

Scenarios	Censored? (Yes/No)	Computation of Time to Discontinuation of IV opioid (in hours)
(iv) Subject does not have any IV opioid data recorded.	No	12:00 (24 hr. clock) on the date of randomization.
(v) Discontinuation from study	Yes	
Time to discontinuation of IV opioids
 
=STOP — START =0 hours; where

		
For treated subjects, STOP and START are both equal to the date and time of the start of the first infusion (loading dose) of study drug, resulting in a value of zero hours for the time to discontinuation of IV opioids.

(vi) Randomized but not treated subjects	No	
For randomized but not treated subjects, STOP and START are both equal to 12:00 (24-hr clock) on the date of randomization, resulting in a value of zero hours for the time to discontinuation of IV opioids.

		
Time to discontinuation of IV opioids
 
= STOP — START; where

		
STOP = 23:59 (24-hr clock) on date of discontinuation from study.

		
START (for treated subjects) = start date and time of the first infusion (loading dose) of study drug.

		
START (for randomized but not treated subjects) = 12:00 (24 hr. clock) on date of randomization

		
Time to discontinuation of IV opioids
 
=STOP — START; where

		
STOP = Stop date and time of latest IV opioid

		
For subjects who have IV opioid records at or after 12:00 (24-hr clock) on the date of randomization:

		
START = 12:00 (24 hr. clock) on the date of randomization

		
For subjects who have no IV opioid records at or after 12:00 (24-hr clock) on the date of randomization:

		
Time to discontinuation of IV opioids = 0 hours.

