1. AMENDMENTS FROM PREVIOUS VERSION(S)

- Status of study when amendment made:

Study protocol amendment 3 was made to use Cohort 1 and Cohort 2 as the primary analysis population. This change was formally endorsed by FDA through a Special Protocol Assessment Modification Agreement Letter (15 April 2019). Study enrollment has been completed on 25 April 2019. The study team has remained blinded. Per protocol, the external Data Monitoring Committee (E-DMC) has reviewed safety data approximately every 6 months since the start of the study. Accordingly, 7 interim safety E-DMC reviews have been completed at the time of this SAP amendment.

- A summary of SAP amendments made prior to the current amendment is provided in **Table 1** below.

Table 1. SAP Version History

SAP Version	Primary Change(s)	Rationale for Primary Change(s)
V1 (dated 12 June 2015)	Not Applicable.	Not Applicable.
V2 (dated 08 March 2016)	[REDACTED]	[REDACTED]
V3 (dated 16 November 2017)	[REDACTED]	[REDACTED]
V4 (dated 7 September 2018)	[REDACTED] [REDACTED] [REDACTED]	[REDACTED] [REDACTED] [REDACTED]

- Specifics on the changes in Version 5 of significance are provided in Table 2 below. These changes are related to the planned Primary Analysis Population and hence are considered significant. In addition, changes were made for editorial reasons (eg, to improve flow, to correct typographical errors, to remove redundancies or improve clarity). These do not represent changes in the statistical objectives or in the planned analyses from the previous version and therefore are not listed in the table below:

Table 2. Summary of Changes in this Amendment from Previous Amendment

Location of Change	Details of Change(s)	Rationale for change(s)
Primary analysis population	Changed the primary analysis population from Cohort 1 to Cohort 1 and Cohort 2 combined.	Combining the two cohorts of subjects would allow for the powered primary efficacy analysis to be undertaken in the entire study population of subjects aged 6 years and above, rather than just in the subjects aged 12 years and above in Cohort 1.
Imputation rules for missing stop date/time	Replaced “withdrawal of consent” with “discontinuation from study”.	For completeness, clarity and consistency.
Section 7.1 TTRFD	Added rules for handling missing data due to discontinuation from study in Table 6.	For completeness, clarity and consistency.

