7.1. TTRFD

Table 6. Handling of Missing TTRFD data components and Censoring Rules

Scenario	TTRFD Censored (Yes/No)	Computation of TTRFD (in hours)
(i) C1 and/or C2 are never met For a treated subject, the date and time corresponding to C1 and/or C2 used in the computation of the censored TTRFD will be the date and time of the last RFD assessment when C1 and/or C2 are still unmet.	Yes	The dates and time for the unmet criteria from C1-C6, will be determined using Section the first column in this table. Dates and time for the met criteria from C1-C6, will be determined using Table 5 . TTRFD = STOP—START; where
(ii) C3, C4, C5, and/or C6 are never met (subject did not discontinue from the study): Start date and time of the latest IV concomitant drug administration is recorded but the stop date and time is missing. For a treated subject, if any applicable criterion among C3-C6, has the latest start date and time for the last administration (of IV concomitant drug) present but the corresponding stop date and time is missing, then that criterion is considered not met. In this case, the time corresponding to the unmet criterion, to be used in the computation of the censored TTRFD, will be the start date and time for the last administration (of IV concomitant drug).	Yes	STOP = Latest date and time among the dates and times for the met or unmet criteria from C1- C6; START = Start date and time of 1 st infusion (loading dose) of study drug.
(iii) Death before RFD criteria met If a treated subject dies in the hospital before RFD criteria are met, then TTRFD will be censored. For C1and/or C2, that was not met prior to death, the time used in the computation of censored TTRFD, will be as described in (i) above. For any of the criteria C3-C6 where death occurred prior to the recording of latest stop date and time of the corresponding IV concomitant drug, the date and time of death will be used as the date and time	Yes	

Scenario	TTRFD Censored (Yes/No)	Computation of TTRFD (in hours)
where the specific criterion was not met.		
(iv) C3, C4, C5, and/or C6 are never met due to discontinuation from the study: Start date and time of the latest IV concomitant drug administration is recorded but the stop date and time is missing.	Yes	

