For a treated subject, if any applicable criterion among C3-C6, has the latest start date and time for the last administration (of IV concomitant drug) present but the corresponding stop date and time missing due to discontinuation from the study, then that criterion is considered not met. In this case, the time corresponding to the unmet criterion, to be used in the computation of the censored TTRFD, will be 23:59 on the date of discontinuation from study.		
(v) Randomized and treated subjects with no data on C1-C6	Yes	TTRFD = 0 hours.
(vi) Randomized but not treated subjects [need to check if there is IV concomitant drug use based on eCRF data at or after 12:00 (24-hr clock) on the randomization date]	Yes	TTRFD = STOP—START; where
In the case of missing stop date/time in any of C3-C6 due to discontinuation from the study, the criterion is considered not met. The date/time of the unmet criterion will be 23:59 on the date of discontinuation from study.		STOP = Latest date and time among the dates and times for the met or unmet criteria from C3- C6 (data are not collected on C1 and C2 for untreated subjects);
For subjects who have no IV concomitant drug use based on eCRF data at or after 12:00 (24-hr clock) on the date of randomization, the criterion C3 is considered met at 12:00 (24-hr clock) on the date of randomization. Criteria C4-C6 are considered NA.		For subjects who have IV records at or after 12:00 (24-hr clock) on the date of randomization:
(vii) C3, C4, C5, C6: Latest stop date present, stop time missing	No	START = 12:00 (24-hr. clock) on the date of randomization
If the stop time is missing, but the corresponding stop date (for any IV concomitant drug administration) is available, the missing stop time will be imputed at 23:59 (24-hr clock), and this criterion will be considered met.		For subjects who have no IV records at or after 12:00 (24-hr clock) on the date of randomization:

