7.2. Time to Discharge

Table 7. Handling of Missing Data and Censoring Rules for Time to Discharge

Scenarios	Censored? (Yes/No)	Computation of Time to Discharge (in hours)
(i) Death prior to issue of discharge order Subject dies in the hospital prior to issue of the hospital discharge order.	Yes	
Time to discharge
 
= (Date and time of subject's death) — (Date and time of start of the first infusion [loading dose] of study drug)

(ii) Discharge order date present, discharge order time missing If the discharge order date is present but the discharge order time is missing, the missing time will be imputed as 23:59 on the date of the discharge order.	No	
Time to discharge
 
= (23:59 [24-hr clock] on the date of the discharge order)
 
— (Date and time of start of the first infusion [loading dose] of study drug)

(iii) Randomized, treated or untreated subjects who are not hospitalized	Yes	
Time to discharge = 0 hours

(iv) Subject discontinuation from study resulting in missing discharge order date and time	Yes	
For randomized and treated subjects:
 
Time to discharge
 
= (23:59 on the date of discontinuation from study)
 
— (Date and time of start of the first infusion of study drug)
 
For randomized subjects who are not treated:
 
Time to discharge
 
= (23:59 on date of discontinuation from study)
 
— (12:00 [24 hr. clock] on the date of randomization)

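### SAP Table 8 censors at death or study discontinuation without requiring a missing final IV-opioid stop, and has no 0 h rule for treated subjects whose IV opioids ended before the loading dose

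*SAP*

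**What the plan says.** SAP 7.4, Table 8, sets the censoring rules for this endpoint. The extracted table is displaced, so cells are matched to rows here by content; the displacement is not counted as an error.

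- Row (i), death, is censored: "STOP = Date and time of subject's death".
- Row "v) Discontinuation from study" is censored: "STOP = 23:59 (24-hr clock) on date of discontinuation from study". It gives a start time for treated and for untreated subjects.
- Row (iii) covers a missing final stop in a subject who stayed in the study.
- Row (iv) gives 0 h, as an event, to a subject with no IV-opioid data.
- Row (vi) covers subjects randomized but not treated. It is marked not censored and uses the latest IV-opioid stop, or 0 h if there is no record from 12:00 on the randomization date.

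The sister tables attach a condition to the same two scenarios. In Table 6 (SAP 7.1), the death time is used for C3 to C6 only "where death occurred prior to the recording of latest stop date and time of the corresponding IV concomitant drug", and the discontinuation date only with "the corresponding stop date and time missing due to discontinuation from the study". In Table 7 (SAP 7.2) the rows read "i) Death prior to issue of discharge order" and "iv) Subject discontinuation from study resulting in missing discharge order date and time".

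The endpoint formula in SAP 6.1.2 is the latest IV-opioid stop minus the start of the loading dose, with no floor at zero. Table 5 (SAP 6.1.1) does set a floor for C3: opioid use that ended before the loading dose counts as met at the loading-dose start.

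**The concern.** C3 and this endpoint rest on the same recorded stop, yet under the literal text they can disagree for one subject. Protocol 6.6 defines discontinuation as ceasing participation at any point before the protocol is completed, and it provides for subjects withdrawn after discharge. So a subject can have a documented final opioid stop and discontinue later. Literal row (v) then replaces a known event by a censored time after it, and keeps the subject in risk sets where he or she does not belong.

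At stake is the last of the four tests in the fixed sequence (Protocol 9.2.2), together with the Kaplan-Meier mean difference, which SAP 8.1.1 names as the primary estimate of the difference in mean times. Misplaced late censoring costs power and adds noise. If such exits differ between arms, the test is biased against the arm with more of them.

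The second gap is smaller. Protocol Table 1, footnote l, has IV opioids recorded from before the first dose. A treated subject with only pre-dose opioids therefore has data, so row (iv) does not apply, and the formula returns a negative time.

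**Working it through.** **Row against row**

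| Situation | Table 6 (C3) | Table 7 | Table 8 as written |
|---|---|---|---|
| Death | only if no final stop was recorded | only if before the discharge order | no condition |
| Discontinuation | only if the stop is missing as a result | only if the order is missing as a result | no condition |
| Opioids ended before loading dose, treated | 0 h (Table 5) | not applicable | not covered |
| Untreated, documented stop, then discontinues | not needed | not needed | (v) censored and (vi) event |

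**Single subjects (assumed times).** Final stop at 100 h, discharge at 110 h, discontinuation dated 60 days after discharge. C3 is met at 100 h. Literal row (v) censors at about 110 + 60 × 24 = 1,550 h. With the condition, the subject is an event at 100 h. For a treated subject whose last opioid stopped 3 h before the loading dose, the formula gives −3 h; the Table 5 rule would give 0 h.

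**The plan's own figure first.** SAP 4.1 has exponential times to readiness-for-discharge, medians 156 and 106 h, two-sided alpha 0.05 and power 0.90. Then ln(156/106) = 0.3864, and the Schoenfeld count is 4 × (1.960 + 1.282)² / 0.3864² = 281.5, so 282 events, as stated. These are figures for the primary endpoint. The documents give no median, effect or power for time to discontinuation of IV opioids.

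**Illustration of the literal row (v).** 6,000 simulated trials per scenario, 150 per arm, the borrowed medians, unstratified two-sided log-rank at 0.05. Each subject leaves with an assumed probability after the documented stop and is censored at stop plus a uniform delay. With no exits, power is 0.91. With equal exit in both arms:

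| Delay after stop | 1% | 2% | 5% |
|---|---|---|---|
| 0–24 h | 0.91 | 0.91 | 0.88 |
| 24–840 h | 0.88 | 0.84 | 0.74 |
| 35–60 days | 0.84 | 0.77 | 0.61 |

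Repeat runs differ by 0.01 to 0.02. The last line needs a recorded discontinuation date that late. Loss of events alone explains little: 282 × 0.95 = 268 events still gives Schoenfeld power 0.886. Most of the fall comes from subjects held in late risk sets.

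At 5% equal exit, the hazard ratio (placebo/rivipansel) moves from 0.68 to 0.73 (24–840 h) or 0.77 (35–60 days). The sampling SD of the Kaplan-Meier mean difference rises from 22.5 h to 31.9 h or 50.9 h.

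**Type I error (156 h in both arms).** With equal 5% exit, rejection is 0.048 to 0.053. With 3% v 5% it is about 0.07 (24–840 h) and 0.09 (35–60 days). With 2% v 6% it is about 0.14 and 0.21 for those windows. With 1% v 2% it stays at about 0.05 to 0.06.

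Deaths were not simulated. No rate exists for opioid stops before the loading dose, so no size is given for the 0 h case.

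**The case against.** The strongest reply is that the SAP already supplies the condition. Section 7 is about missing values, and Table 8's title says so too. Row (iii) limits itself to subjects who did not discontinue, which makes sense only if row (v) is its complement: a stop missing because the subject left. The introduction to section 7 uses the discontinuation time only where a derivation needs it, and a recorded stop removes the need. Section 7.3 sends the reader to Table 8 when the final stop is missing. The change table in SAP section 1 labels the related edit "Imputation rules for missing stop date/time". This largely stands: the missing-stop reading is the probable one, and under it the loss is nil. It does not remove the gap. The table's title also covers censoring rules in general, and rows (v) and (vi) give opposite status to the same untreated subject with no stated precedence.

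The reply is also right that exit rates, delays and imbalance are assumed. The larger error rates need about 3 v 9 exits of 150 per arm, which nothing in the documents suggests. Row (i) has no shown consequence: the Phase 2 summary in Protocol 1.2.3 reports no deaths. On the pre-dose case, section 7 starts measurement at the first infusion, and Table 5 and row (vi) both point to 0 h. That is a fair inference, but no row states it for treated subjects.

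A reader might infer that the SAP instructs programmers to discard recorded stops, or that its type I error control is broken. The documents support neither. The context points the other way, and no exit rate, let alone an imbalance between arms, is given.

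**Conclusion.** The gap in the text is real; the harm is conditional. Table 8 rows (i) and (v) lack a condition that the sponsor's own Tables 6 and 7 state, rows (v) and (vi) overlap, and one class of treated subjects has no valid value. The primary endpoint is untouched, because Table 6 carries the condition for C3.

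The size runs from nothing, under the probable intent, to the illustrated loss if the rows are programmed as they stand. That loss rests on borrowed medians and on assumed exit rates and delays, so it shows scale only. It is not a shortfall against a design value, since none is stated for this endpoint, which is formally tested only if the three before it succeed. Severity: minor. It is worth correcting because the endpoint is alpha-controlled and the correction costs almost nothing.

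**What to change.** Amend Table 8 before unblinding:

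1. Row (i): death before a documented final IV-opioid stop.
2. Row (v): discontinuation from the study resulting in a missing final IV-opioid stop. State that a documented stop takes precedence, which also settles the overlap with row (vi).
3. New row: a treated subject whose last IV-opioid stop precedes the loading dose is an event at 0 h, matching Table 5 for C3.

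The cost is three lines of SAP text and the matching lines of derivation code. No new data are needed. SAP section 1 records the study team as blinded at the time of this version.

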8. STATISTICAL METHODOLOGY AND STATISTICAL ANALYSES

8.1. Statistical Methods

All analyses will be conducted for Cohort 1 and Cohort 2 combined, Cohort 1 by age group and Cohort 2 separately. Analyses of TTRFD will also be conducted for Cohort 1 alone. In general, counts and percentages will be presented for categorical variables. The number of non-missing observations, mean, standard deviation (standard error of the mean), median, minimum, and maximum will be presented for continuous variables. In addition, graphical displays will be used when appropriate.

8.1.1. Analysis for Time-to-Event Data

Kaplan-Meier product limit method will be used to estimate median with 95% confidence interval and mean time for time-to-event endpoints and to produce a graphical representation of the distribution of time-to response. Difference between treatment median times, estimated mean times with standard error (SE) and the 95% confidence interval (CI) of difference between treatment means will be reported. This difference between the treatment mean times will be considered as the primary estimate for treatment difference in mean times to event.

In addition, the following two supportive mean estimates that are restricted to a cut-off time will be reported with SE, difference between treatment means and the corresponding 95% CI (See Appendix 10.5 for more details):

- **Restricted mean** with cut-off time equal to the minimum of the maximum observed times in the two treatment groups (based on the restricted mean survival time [RMST] methodology)
- **Modified restricted mean** with cut-off time equal to the maximum of the maximum observed times in the two treatment groups

A stratified log-rank test where the stratification variables are Age Group (3 age groups: two in Cohort 1 and one in Cohort 2) and Genotype will be performed for the primary analysis population (Cohort 1 and Cohort 2 combined) to test for differences between the rivipansel and placebo treatment groups.

For each analysis, a Cox regression model with Age Group (for analyses of Cohort 1 and Cohort 2 combined and of Cohort 1 alone) and Genotype (for all analysis groups) as stratification variables will be used to estimate the hazard ratio (HR, placebo rate divided by rivipansel rate) and the corresponding two-sided 95% CI. Note that the HR will be placebo/rivipansel since for data in exponential distributions the HR is equivalent to the reversed ratio of treatment median times to event.

Counts and percentages of subjects who experienced the event as well as counts and percentages of subjects who were censored and the type of censoring (eg, death or missing data) will be reported for each of the treatment groups.

